5.0 Study Intervention/Investigational Agent

5.1 Description:

This study is neither a drug nor a device trial. Patients will be administered FDA approved ICG through intravenous injection and imaged by a FDA approved surgical fluorescence imaging device (Spy Elite or SPY PHI or Medtronic EleVision) which is 0.5 meter away from the subject. Both ICG fluorescence and the imaging system have been used for routine clinical practice for many years. ICG fluorescence imaging utilizes intravenously injected ICG, which is a fluorescent dye that is FDA-approved for clinical use, illuminated with near-infrared light. The ICG dye is indirectly activated and the dynamic fluorescence due to tendon perfusion can be captured by a video rate imaging system. The subscapularis takedown technique will alternate between tenotomy and peel for every other patient taken to the operating room. There is no reason intraoperatively to choose one technique over the other and therefore this puts

PROTOCOL TITLE: Pilot feasibility study of dynamic contrast-enhanced fluorescence imaging to guide total shoulder arthroplasty approach

the patient at no added risk. If the surgeon feels that neither of these techniques are appropriate for the treatment of the patient then the patient will not be approached for enrollment.

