2.0 Objectives

The purpose of this pilot study is to evaluate the feasibility of open, wide-field imaging of indocyanine green ingress and egress during total shoulder arthroplasty.

The long-term goal of this work is to use DCE-FA for the assessment of subscapularis tendon perfusion and to determine potential relationships between perfusion and patient reported outcomes and subscapularis failure.

Primary Research Question:

To what degree does the relative perfusion of the subscapularis tendon—measured using DCE-FI—change after tenotomy vs peel technique and subsequent intra-operative repair?

Hypothesis: Perfusion of the subscapularis tendon will be reduced from baseline after tenotomy and peel techniques during shoulder arthroplasty.

Secondary Question:

Does DCE-FI with indocyanine green, used in a real time, intra-operative setting, highlight technique-dependent variations in subscapularis tendon perfusion during shoulder arthroplasty?

Aim: To determine if intra-operative ICG administration during shoulder arthroplasty can be coupled with an intra-operative surgical fluorescence detection device to determine alterations in subscapularis tendon perfusion before and after repair using peel and tenotomy takedown techniques for a deltopectoral approach.

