The indocyanine green based DCE-FI will NOT be used to guide treatment or patient care. The data acquired using the SPY Elite or SPY PHI or EleVision will be anonymized and exported to a secure PC for additional analysis and processing. The analysis techniques will be more sophisticated than the current commercial system, and involve a correction for the patient-specific arterial input function (AIF) (Elliott *et al.*, 2020)—the cardiac and circulatory variations that can modify the time and manner in which the ICG dye arrives in the imaging field-of-view.

Indocyanine green (ICG) is a well-studied water soluble, light absorbing tracer that has been used in other capacities to help quantify tissue perfusion during

PROTOCOL TITLE: Pilot feasibility study of dynamic contrast-enhanced fluorescence imaging to guide total shoulder arthroplasty approach

surgery. ICG is able to be injected into a patient intravenously and subsequently circulate systemically while bound to albumin, quickly undergoing hepatic metabolism in just several minutes (Faybik and Hetz, 2006). The concentration of ICG in specific tissue is able to be quantified as a surrogate for tissue perfusion. ICG due to its IV administration and quick metabolism is able to help quantify perfusion in real time, such as intra-operatively (Lutken *et al.*, 2021). Systemic reviews as well as case studies, most commonly in plastic surgery, have been performed showing its utility to determine adequate or inadequate perfusion in downstream tissue in situations where microanastomoses are performed, such as with flaps (Krishnan *et al.*, 2005) and in hand surgery (Li *et al.*, 2018). Other studies have also been conducted showing the ability to use ICG as a surrogate for tissue perfusion in the achilles paratenon in humans and in rabbits who had undergone rotator cuff repair to determine tissue perfusion after different types of repair. The use of ICG imaging in orthopaedic surgery is relatively nascent, and our institution (Gitajn *et al.*, 2020) as well as other collaborators (Sepehri *et al.*, 2021) have demonstrated its promise in these applications.

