4.0 Study Endpoints*

Primary end point:

To assess the technology and its ability to see blood supply in the subscapularis tendon before takedown and after employed repair. The benchmark for this is the rise and fall of fluorescence signal approximately 10-40 seconds after injection. Given our experience in DCE-FI for bone fractures, it will be more or less self-evident whether the DCE-FA signal is sufficient for further analysis.

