6.0 Procedures Involved*

The research design for this study is a single cohort longitudinal study employing a consecutive sampling methodology. Eligible patients regardless of ethnicity or health

PROTOCOL TITLE: Pilot feasibility study of dynamic contrast-enhanced fluorescence imaging to guide total shoulder arthroplasty approach

status, will be identified and recruited subject to inclusion and exclusion criteria listed in section 10. Patients who meet eligibility criteria will be asked to participate in the trial. If they agree written informed consent will be obtained from the patient or their legal authorized representative. To obtain informed consent, study personnel (surgeon or research coordinator) will adhere to the following procedures: (1) present study information in a manner that is understandable to the patient; (2) discuss the study with the patient and answer any questions; (3) allow the patient an opportunity to discuss participation with their family; (4) confirm that the patient understands the risks and benefits of participating in the study and that their participation is voluntary; (5) complete the consent process and obtain signatures from the patient and research team. The process of obtaining and documenting informed consent forms will be completed in accordance with local Good Clinical Practice (GCP) recommendations.

If the research team member obtaining consent is at all unsure about the patient's ability to consent, s/he will consult with the study PI.

Patients will be randomized to undergo either a subscapularis peel or subscapularis tenotomy.

Recognizing that consent is an ongoing process, the study team will encourage the participants to ask additional questions that may arise during the course of their participation in the study.

On the surgery day, the patient will be prepared and transported to surgery as per routine at Dartmouth-Hitchcock. In the OR, patient positioning, preparation of the surgical field, and draping will follow standard practice for arthroplasty of the involved shoulder joint.

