A Pulse dye densometer (PDD; in-house developed), similar to a pulse oximetry probe, which is used clinically both in the operating room, in inpatients as well as outpatients to assess oxygen saturation. This is completely non-invasive. In the context of this study the pulse dye densometer collects data on the ICG injection parameters so that the kinetic curves can be normalized to injection-related differences. The PDD will be placed on the patient's finger to acquire an arterial blood input function during ICG injection.

After the subscapularis tendon is visualized during the surgical approach, 0.1 mg/kg ICG will be injected intravenously. Video rate ICG fluorescence images will be acquired 20 seconds before and 4 minutes after ICG injection. This process will be repeated towards the end of the procedure after the subscapularis is repaired, but prior to skin closure.

ICG will be administered by an anesthetist in the operating room. Patients are under the care and observation of the anesthesia and surgical teams during this time. Postoperatively, patients are transferred to the Post-Anesthesia Care Unit (PACU) where they are monitored

PROTOCOL TITLE: Pilot feasibility study of dynamic contrast-enhanced fluorescence imaging to guide total shoulder arthroplasty approach

continuously by nursing staff supervised by anesthesiologists. During this entire time vital signs (including temperature, pulse, respiratory rate and blood pressure) are collected as standard of care. All clinical data will be reviewed for adverse events for a period of 30 minutes post-injection.

Day of surgery Procedures	Pre-Infusion	0-30 minutes post-infusion
Pulse	X	X
Blood Pressure	X	X
Temperature	X	X
Respiratory Rate	X	X
Adverse Events		X

Study patients will be seen per usual protocol for wound assessment and general health assessment after their shoulder arthroplasty at approximately 4 weeks post operatively.

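### Does permitting three fluorescence cameras, with no written rule to hold camera and settings between a patient's two acquisitions, undermine the before/after perfusion comparison?

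*Protocol*

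**What the plan says.** Two places in the Protocol name the cameras. Section 5.1 has patients imaged by one FDA-approved "surgical fluorescence imaging device (Spy Elite or SPY PHI or Medtronic EleVision", at a working distance of 0.5 m. Section 3.0 says "The data acquired using the SPY Elite or SPY PHI or EleVision will be anonymized and exported to a secure PC" for further processing. Neither gives a rule for choosing among the three.

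Sections 5.3 and 6.0 fix the rest of the acquisition: 0.1 mg/kg ICG per injection and video-rate images from 20 seconds before to 4 minutes after injection. The same sequence is then carried out once more after the repair and before skin closure. Unit, gain, exposure and illumination are not mentioned.

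Two corrections are described. Section 3.0 corrects for the patient's arterial input function. Section 6.0 adds the pulse dye densitometer, "so that the kinetic curves can be normalized to injection-related differences". Both deal with the delivery and arrival of dye, not with the response of the camera.

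The quantitative question is in section 2.0: to what degree relative perfusion will "change after tenotomy vs peel technique and subsequent intra-operative repair". The hypothesis is "Perfusion of the subscapularis tendon will be reduced from baseline after tenotomy and peel techniques during shoulder arthroplasty". The only end point, in section 4.0, is qualitative: "The benchmark for this is the rise and fall of fluorescence signal approximately 10-40 seconds after injection".

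**The concern.** A fluorescence intensity depends on the camera as well as on the tissue. If the camera or its settings differed between the two acquisitions in a patient, the change in response would be read as a change in perfusion. It could point in the hypothesised direction: with no true change, a response 20% lower at the second acquisition looks like a 20% fall. It could also hide a real fall: a true ratio of 0.80 with a response factor of 1.25 is measured as 0.80 × 1.25 = 1.00.

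A second route is between techniques. If camera models differ in offset, saturation or linearity, and one model is used more often with peel than with tenotomy, the technique comparison could carry part of that difference. Neither stated correction would remove either effect, and clipped signal or unrecorded settings cannot be recovered in analysis. The matter therefore cannot simply be left to a statistical analysis plan.

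**Working it through.** The Protocol gives no camera-response figure, effect size or standard deviation, so there is no stated figure to reproduce. The camera inputs below are assumptions.

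**1. What the text implies.** Section 5.1 uses the singular for the imaging device and then refers back to it as one system. Sections 5.3 and 6.0 have the sequence repeated in the same operation. The list of three reads as whichever system is available for a case. A switch of camera in mid-operation is possible but is not what the text suggests.

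**2. Before/after ratio in one patient.** Take a true after/before ratio r = 0.60 and let g be the camera response at the second acquisition divided by that at the first. The measured ratio is r × g.
- Same camera and settings, linear response: g = 1, ratio 0.60, no bias, whichever camera is used.
- Response changed in mid-case: g = 0.8 gives 0.60 × 0.8 = 0.48; g = 1.25 gives 0.60 × 1.25 = 0.75.

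**3. Effect on the group.** If k of n patients are affected, the geometric mean ratio shifts by exp[(k/n) ln g] − 1. With g = 0.8:
- 3 of all 10 patients: exp(0.3 × ln 0.8) − 1 = −6.5%.
- 2 of 5 in one technique and none in the other: exp(0.4 × ln 0.8) − 1 = −8.5% in the between-technique ratio.

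These shifts need a real change of response in mid-case. The second also needs such changes to fall in one technique only.

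**4. Offset and clipping with one camera held.**
- An offset o, as a fraction of baseline peak, gives (0.60 + o)/(1 + o): 0.62 for o = 0.05 and 0.67 for o = 0.20. The 20 seconds of pre-injection images at each acquisition allow a constant offset to be subtracted, which restores 0.60.
- A baseline peak clipped at a fraction c of its height gives 0.60/c: 0.67 for c = 0.9 and 0.75 for c = 0.8.

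Both would arise in a study with a single camera. Neither is caused by permitting three, and holding unit and settings would not in itself remove either.

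**5. Technique comparison, camera held within each patient.** The false difference is (difference in the number of patients per technique imaged on that camera ÷ 5) × bias. The biases from step 4 are 0.019 to 0.067 for offset and 0.067 to 0.15 for clipping.
- Difference of 1 patient: 0.019/5 = 0.004 up to 0.15/5 = 0.03.
- Difference of 2 patients: 0.008 up to 0.06.

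**6. How likely a difference of 2 or more is.** Section 5.1 says "The subscapularis takedown technique will alternate between tenotomy and peel for every other patient taken to the operating room"; section 6.0 says "Patients will be randomized to undergo either a subscapularis peel or subscapularis tenotomy". That conflict is a separate matter, so both were worked out for five patients per technique.
- Strict alternation, each camera used in one run of consecutive patients: such a run splits between techniques with a difference of at most 1, so the probability is 0%.
- Randomization 5:5, one changeover after patient k: 44% for k = 2 or 8 (20/45); 17% for 3 or 7 (20/120); 52% for 4 or 6 (1 − 100/210); 21% for 5 (1 − 200/252).
- Camera drawn independently for each patient: 22% (two cameras, 80:20), 34% (50:50), 56% (three in equal shares).

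**7. Feasibility end point.** A rise and fall in time keeps its shape and timing under a linear gain. It would be affected only near the detection limit or at saturation, and the documents give no sensitivity data on either.

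**The case for a change.** The strongest case for a change is that the question in section 2.0 is quantitative, that the Protocol itself accepts that raw signal needs correcting, and that the correction stops short of the camera. Distance, dose and timing are written down; camera settings are not. A sentence requiring the same unit and settings, and one data field per acquisition, would cost almost nothing, and a later study may build on these ratios.

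It stands that no same-unit, same-settings rule is written and that a mid-case change would bias that patient's ratio. It does not follow that the plan leads analysts wrong. The section 4.0 benchmark is judged from the investigators' stated experience of this imaging in bone fractures, and section 5.3 refers to an earlier pilot at the institution. Holding the camera between two images that are to be compared is ordinary practice, so the sentence would only record it.

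Stricter versions gain little or carry a cost. The peak signal is unknown before the first injection, so settings locked at baseline could lock in clipping, or leave a weak post-repair signal too dim for the section 4.0 benchmark. One model for all ten patients depends on which equipment is free. Introducing models in tenotomy/peel pairs guards against a false difference of at most 0.06 under the assumptions used.

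The ratio of peak heights used here is itself an assumption. The Protocol speaks of relative perfusion and corrected kinetic curves, and measures based on timing would not scale with gain.

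**Conclusion.** The concern identifies a real silence but not a fault that calls for a change. On the ordinary reading of sections 5.1, 5.3 and 6.0, one camera serves both acquisitions in a patient, and a constant gain then drops out of the after/before ratio. Distortion of the order of 0.48 to 0.75 around a true 0.60 requires response to change in mid-case by an assumed factor of 0.8 to 1.25, which nothing in the Protocol prescribes or suggests. The mix of cameras across techniques contributes 0.004 to 0.06 on assumed offsets and clipping. The stated primary objective and the only end point concern feasibility, are little affected, and belong to a 10-patient pilot whose images do not guide care.

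The conclusion rests on three assumptions: one device per operation, a response close to linear below saturation, and settings that the imaging team holds or notes in the usual way. Writing that practice down would be harmless and optional.

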1.0 Study Summary

Study Title	Pilot feasibility study of dynamic contrast-enhanced fluorescence imaging to guide total shoulder arthroplasty approach
Study Design	Cross sectional study
Primary Objective	To evaluate the feasibility of open wide-field imaging of indocyanine green ingress and egress during total shoulder arthroplasty.
Secondary Objective(s)	To characterize the relationship between tissue perfusion measured with DCE-FI and different approaches and techniques used in total shoulder arthroplasty.
Research Intervention(s)/Investigational Agent(s)	Assignment of research participants to subscapularis peel or tenotomy techniques utilized during total shoulder arthroplasty surgical approach. Indocyanine Green (ICG) indicated for soft-tissue perfusion assessment
IND/IDE #	N/A
Study Population	Patients who are undergoing open surgery for shoulder arthroplasty
Sample Size	10 patients
Study Duration for individual participants	4-6 weeks
Study Specific Abbreviations/Definitions	AIF: arterial input function CDC: Centers for Disease Control and Prevention CRF: Case Report Forms DCE-FA: Dynamic Contrast Enhanced Fluorescence Arthroscopy DCE-FI: Dynamic Contrast Enhanced Fluorescence Imaging DoD: US Department of Defense D-HH: Dartmouth-Hitchcock Health DHMC: Dartmouth Hitchcock Medical Center FI: fluorescence imaging GCP: Good Clinical Practice GFR: glomerular filtration rate HRPP: Human Research Protection Program ICG: Indocyanine Green NSF: nephrogenic sclerosing fibrosis PDD: Pulse Dye Densitometer ROI: Region of interest SSI: Surgical Site Infection

PROTOCOL TITLE: Pilot feasibility study of dynamic contrast-enhanced fluorescence imaging to guide total shoulder arthroplasty approach

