10.0 Inclusion and Exclusion Criteria*

PROTOCOL TITLE: Pilot feasibility study of dynamic contrast-enhanced fluorescence imaging to guide total shoulder arthroplasty approach

The clinical schedule of the orthopaedic surgeon who is the principal investigator will be reviewed by members of the research team for eligible study participants. Identified patients who meet inclusion criteria for the study will be provided information about the study by the orthopaedic surgeon, or a qualified member of their care team, at the time of their pre-operative clinic visit. Patients who wish to participate in the study will then undergo an informed consent process for the study.

Inclusion criteria:

- a. Participant must be 18 years of age or older
- b. Meet clinical and radiographic parameters necessary to undergo shoulder arthroplasty
- c. Subscapularis tendon intact clinically on exam or via advanced imaging
- d. Subject has the ability to have their shoulder arthroplasty completed using either the tenotomy or peel technique.

Exclusion criteria:

- a. Inability of patient to provide informed consent
- b. Iodine allergy
- c. Subscapularis tendon tear or concern for tear
- d. Incarceration
- e. Pregnant women
- f. Patients less than 18 years of age
- g. Prior deltopectoral approach to the ipsilateral shoulder

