12.0 Local Number of Subjects

All 10 patients will be enrolled at this facility by the primary surgeon. This is a modest number of subjects to allow us to properly evaluate the feasibility of evaluating subscapularis tendon perfusion by two different takedown techniques in shoulder arthroplasty.

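### Section 5.1 allocates the takedown technique by strict alternation, Section 6.0 says patients are randomized; alternation is predictable and leaves the peel–tenotomy contrast open to selection bias

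*Protocol*

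**What the plan says.** The protocol describes the allocation of technique in three places.

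- Section 1.0 makes allocation part of the research intervention: "Assignment of research participants to subscapularis peel or tenotomy techniques utilized during total shoulder arthroplasty surgical approach".
- Section 5.1 gives a deterministic rule tied to operating order: "The subscapularis takedown technique will alternate between tenotomy and peel for every other patient taken to the operating room".
- Section 6.0 gives a different method: "Patients will be randomized to undergo either a subscapularis peel or subscapularis tenotomy". The same section calls the study a "single cohort longitudinal study employing a consecutive sampling methodology".

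No section describes a random sequence or any concealment.

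On who selects patients, Section 12.0 says: "All 10 patients will be enrolled at this facility by the primary surgeon". Section 5.1 adds a screen based on the surgeon's judgement: "If the surgeon feels that neither of these techniques are appropriate for the treatment of the patient", the patient is not approached. Inclusion criterion d in Section 10.0 is worded differently: "Subject has the ability to have their shoulder arthroplasty completed using either the tenotomy or peel technique". Sections 10.0 and 13.0 place the approach and enrolment in clinic, before surgery. Section 5.3 calls the study open label.

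The contrast between techniques is part of the primary research question in Section 2.0. The secondary question there asks about "technique-dependent variations in subscapularis tendon perfusion during shoulder arthroplasty".

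**The concern.** Staff who follow Section 5.1 will alternate. An author who follows Section 6.0 will report a randomized study. If alternation is what is done, that report would be wrong on a basic feature of the design.

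The practical difference is predictability. Under alternation, each assignment follows from the one before it. Whoever knows the operating order knows which technique comes next, and could decide whether to approach a patient, or where to place a case, with that knowledge. The two groups could then differ in ways unrelated to technique.

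This matters because Section 3.0 says that a perfusion difference after repair could be a reason to prefer one technique. The contrast is therefore meant to be interpreted, and how far it can be trusted depends on how patients came to be in each group.

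**Working it through.** The protocol gives no figure to reproduce here. The total of 10 is justified by feasibility, without alpha, power or effect size. The check sets the two sentences side by side and then measures how predictable each method is.

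**The two sentences.** A patient's technique is either fixed by place in the operating order (5.1) or drawn at random (6.0). The choice belongs to the protocol, and a separate analysis plan could not make both statements true.

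**Inputs.** Total of 10 patients (Sections 1.0, 5.3 and 12.0). Alternation of 10 gives 5 per technique. The surgeon sees past assignments, because the study is open label. The figures for alternation also assume that the operating order is known.

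**Expected correct guesses of the next technique, out of 10, using the best guess each time**

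- Alternation: the first is a coin toss and the other nine are certain, so 0.5 + 9 = 9.5. If the starting technique is announced, 10.
- One concealed 5:5 list, with n = 5 per technique: n + (2^(2n)/C(2n,n) − 1)/2 = 5 + (1024/252 − 1)/2 = 5 + (4.063 − 1)/2 = 6.53.
- Concealed simple randomization: 10 × 0.5 = 5.0. It gives exactly 5:5 only 252/1024 = 24.6% of the time.

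**Assignments certain before they are made**

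- Alternation: 9 of 10.
- One 5:5 list: an assignment is certain only once the other technique is used up. The expected number is 2n/(n + 1) = 10/6 = 1.67.

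**Dependence on the operating order.** Enrolment is in clinic, while alternation runs by order of surgery, and the documents do not say how much of that order is settled at the approach. If none of it is known and either technique is equally likely, guesses at approach are right 10 × 0.5 = 5 times in 10. If all of it is known, 9.5 to 10. The true figure lies in that range.

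**Sensitivity of a 5 versus 5 comparison.** If two patients with values x and y trade places, one group mean moves by (y − x)/5 and the other by −(y − x)/5. The difference in means moves by 2(y − x)/5 = 0.4(y − x). This holds for any two groups of five, however formed. It shows how little movement of patients is needed to change the result, and is not a measure of bias under alternation.

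**The case against.** The best case for leaving the design alone has four parts.

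1. *This is a small feasibility pilot.* The endpoint in Section 4.0 is whether the signal can be seen, the hypothesis in Section 2.0 is a fall from baseline after both techniques, and no between-technique test is stated. This is right and limits the scope: neither item depends on allocation. The contrast is still in the primary and secondary questions, and the contradiction stands at any sample size.

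2. *The technique may not be known at approach.* Enrolment precedes surgery, and Sections 10.0 and 13.0 also give research staff and the care team a part in screening. This stands as a condition on the 9-of-10 figure. It does not close the other route, since case order can still be set after consent.

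3. *Safeguards exist.* Consecutive sampling and criterion d narrow the room for steering, and criterion d should exclude a patient suited to only one technique. Both deserve credit, but neither hides the next assignment. The screen in Section 5.1 stops only patients for whom *neither* technique suits, so the two wordings do not match. That is a wording fault rather than a second source of bias.

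4. *Predictability is not bias.* The outcome is change from the patient's own baseline, with correction for arterial input, so steering would have to act on predictors of that change. This is correct: the guess counts show opportunity, and neither the occurrence nor the direction of bias can be read from the documents.

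**Conclusion.** The concern holds. Sections 5.1 and 6.0 state incompatible allocation methods, and if 5.1 is followed the study is not randomized. That part needs no assumption.

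The opening for selection bias is real but conditional. With the operating order known, alternation makes 9 of 10 assignments certain in advance, against an average of 1.67 under one concealed 5:5 list; expected correct guesses are 9.5 (10 with a known start) against 6.53. With about five patients per technique, the comparison is exploratory under either method. The point should be fixed before enrolment, but it does not threaten the feasibility aim.

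**What to change.** Preferred: replace the alternation sentence in Section 5.1 with a computer-generated list of five peels and five tenotomies. Someone outside recruitment prepares and holds it, and each assignment is opened only after consent and eligibility are confirmed. State which order (for example, order of consent) determines a patient's place on the list. One list of 10 is better than small blocks: blocks of 4, 4 and 2, with sizes known, would raise expected correct guesses to 2 × 2.833 + 1.5 = 7.17. Make Section 6.0 refer to the same procedure.

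If alternation is kept: remove *randomized* from Section 6.0, describe allocation as non-randomized by operating order, and label the peel–tenotomy comparison descriptive.

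Either way, bring the *neither* wording in Section 5.1 into line with inclusion criterion d.

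Cost: a 10-line list with sealed envelopes or an electronic equivalent, plus edits to two sections, and no extra patients. The technique becomes known somewhat later. The alternative costs only wording but leaves the contrast descriptive.
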